4 ANALYSIS POPULATIONS

Population	Definition / Criteria	Analyses Evaluated
Screened	
 • Comprise of all subjects who were screened for inclusion into the study and have any value databased in the eCRF. 	
 • Study Population
Enrolled ¹	
 • Comprise of all subjects who were enrolled ie, randomised to study treatment. • Only required for 'Summary of Age Ranges' data display; necessary for disclosure purposes to EudraCT and FDAAA. 	
 • Demographics
All Subjects	
 • Comprise of all subjects who receive at least one dose of study treatment. • This population will be based on the treatment the subject actually received. 	
 • Study Population • Safety • Biomarkers
Run in failures	
 • Comprise of all subjects who were assigned a randomisation number (even if it was assigned in error) but did not receive any doses of study treatment 	
 • Study Population
Modified Intent-To-Treat (mITT)	
 • Comprise of all randomised subjects who receive at least one dose of study treatment and commence a BAC at follow-up. • This population will be based on the treatment the subject received. • Any subject who receives a treatment randomisation number will be considered to have been randomised. 	
 • Efficacy
Per-Protocol (PP)	
 • Comprise of all mITT subjects who comply with the protocol. • Protocol deviations that would exclude subjects from the PP population are defined in Section 4.1 (Protocol Deviations) and Appendix 1 (Protocol Deviation Management and Definition for Per-Protocol Population). 	
 • Efficacy
Pharmacokinetic (PK)	
 • Subjects in the 'All Subjects' Population for whom a pharmacokinetic sample is obtained and analysed. 	
 • Pharmacokinetic
Sputum Producers (Sputum)	
 • Subjects in the 'All Subjects' Population for whom a viable pre- or post-challenge sputum sample is obtained (at Screening). 	
 • Sputum Biomarkers

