
 • Each endpoint will be analysed separately using a Bayesian Mixed effects model fitted within Proc MCMC in SAS using the following approach: • Assume equal variances across treatment arms and use a pooled estimate of residual variability (Note: if the posterior predictive distributions produced to support the interim analysis suggest this assumption may be invalid then the modelling approach may be modified to estimate separate variance terms for each treatment arm). • Step 1: Fit all three of the following models (report output from each model in the same listing – along with the DIC values and changes in DIC values between models). Using a combination of changes in the DIC criteria, and expert judgment (see Section 11.9.1), select a single model. 
 • M1: Intercept + Centre + Treatment + Allergen Exposure + Treatment*Allergen Exposure + Baseline • M2: Intercept + Centre + Treatment + Allergen Exposure + Baseline • M3: Intercept + Centre + Treatment + Baseline • See Section 11.4.2 for Baseline definitions (Screening visit 2 BAC endpoint).

Primary Statistical Analyses

Where in each of the models (M1, M2 and M3) the effects are:

Type	Name (#Levels)	Parameters	Prior(s)
Fixed Categorical	Intercept (1)	#1 Intercept	N (0, Var=1E6)
	Treatment (2)	#1 Placebo	N (0, Var=1E6)
		#2 20ng	n/a (constraint = 0)
	Allergen Exposure (2)	#1 Presumed	N (0, Var=1E6)
		#2 Unknown	n/a (constraint = 0)
	Treatment * Allergen Exposure (4)	#1 Pbo*P	N (0, Var=1E6)
		#2 Pbo*U	n/a (constraint = 0)
		#3 20ng*P	n/a (constraint = 0)
		#4 20ng*U	n/a (constraint = 0)
Fixed Continuous*	Baseline	Baseline slope	N(0, Var=1E6)
Random	Centre (planned 6 centres)	Separate value per contributing centre sampled as i.i.d $\sim N(0, \sigma_{Centre}^2)$	$\sigma_{Centre}^2 \sim \text{Gamma}(\text{Shape}=0.048, \text{Scale}=0.830)$ Weakly informative prior based on 6x in-house GSK datasets – same prior for both endpoints Δ

*=Centre covariates prior to fitting model (do not use observations that will not contribute to the planned model when centering) and if applicable the centering is to occur after any transformations have been applied

Δ =If chain is not mixing (i.e. sticking at values close to zero) an additional mixture prior may be considered to act as a lower boundary constraint, or the centre term excluded from the model.

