11 APPENDICES

Section	Appendix
RAP Section 4 : Analysis Populations	
Section 11.1	Appendix 1 : Protocol Deviation Management and Definitions for Per Protocol Population
RAP Section 5 : General Considerations for Data Analyses & Data Handling Conventions	
Section 11.2	Appendix 2 : Assessment Windows
Section 11.3	Appendix 3 : Treatment States & Phases
Section 11.4	Appendix 4 : Data Display Standards & Handling Conventions 
 • Study Treatment & Sub-group Display Descriptors • Baseline Definitions & Derivations • Reporting Process & Standards
Section 11.5	Appendix 5 : Derived and Transformed Data 
 • General, Study Population & Safety • Efficacy • Pharmacokinetic • Pharmacodynamic and or Biomarkers
Section 11.6	Appendix 6 : Premature Withdrawals & Handling of Missing Data 
 • Premature Withdrawals • Handling of Missing Data
Section 11.7	Appendix 7 : Values of Potential Clinical Importance 
 • Laboratory Values • ECG • Vital Signs
Section 11.8	Appendix 8 : Multicentre Studies
Section 11.9	Appendix 9 : Examination of Covariates and Subgroups
Section 11.10	Appendix 10 : Multiple Comparisons and Multiplicity
Section 11.11	Appendix 11 : Model Checking and Diagnostics for Statistical Analyses
Other RAP Appendices	
Section 11.12	Appendix 12 : Abbreviations & Trade Marks
Section 11.13	Appendix 13 : List of Data Displays
Section 11.14	Appendix 14 : Example Mock Shells for Data Displays (see separate document: RAP-Mock Tables-205540.doc)

11.1 Appendix 1: Protocol Deviation Management and Definitions for Per Protocol Population**11.1.1 Exclusions from Per Protocol Population**

The Protocol Deviation Management Plan (PDMP) contains more detail on the specific items that may cause subjects to be excluded from the per protocol population. In general a subject meeting any of the following criteria is expected to be excluded from the Per Protocol population (as described in the PDMP reviews and decisions will occur on a case by case basis):

Number	Exclusion Description
01	Failure of any inclusion/exclusion criteria, but subject is still enrolled.
02	Subject took short-acting beta-agonist (SABA) more than 2 days per week on average.
03	Subject did not receive all 8 doses of planned medication (Placebo or GSK2245035).

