- If an observation is missing between two non-missing observations, the AUC will be linearly interpolated between the two non-missing values i.e., the subject's profile will be assumed to be linear between the two available values. No imputation will be made if either the first or last observation is missing.
- If the number of missing values is considered to be substantial, or if the data is not considered to be missing at random, a sensitivity analysis will be carried out with respect to methods of handling missing data in the calculation of the weighted mean.
- The weighted mean will be set to missing for the relevant challenge if any of the following occurs:
 - A short-acting inhaled β -agonist is taken within 8 hours at any time prior to the challenge
 - The dose of allergen administered is different to that of the Screening dose. Note that the dose of allergen used during the treatment period may be modified from the total dose received at screening, for safety reasons, at the discretion of the investigator. However, in this case, the modified dose used must be consistent for all follow up visits. [In these cases the baseline will be set to missing.]
 - The weighted mean LAR will be set to missing if the subject took rescue medication prior to the LAR period i.e., between 0 and 4 hours post-saline.
 - If rescue medication is administered during the LAR period prior to the completion of the 10 hour FEV_1 assessment, all FEV_1 values recorded after the administration of rescue medication for that challenge will be set to the last recorded FEV_1 value prior to the administration of rescue medication. The LAR does not have the same natural recovery as the EAR, hence this is the most appropriate derivation for the LAR. The weighted mean LAR will then be calculated as above, using the imputed data set.
 - If the use of rescue medication is widespread and/or appears to follow a trend, appropriate sensitivity analyses to examine the impact of the derivations may be conducted. For example, if a large number of subjects are rescued at around 8 hours, the weighted mean LAR over 4-8 hours may be derived and analysed as a sensitivity analysis. All sensitivity analyses will be documented in the CPSR.
 - There may be other conditions that effect the LAR response. In such situations it may be necessary to set the respective response to missing. Such scenarios will be

LAR and EAR

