identified and documented before unblinding or DBF. Appropriate, sensitivity analyses may be conducted if other situations are noted following unblinding or DBF.
Minimum LAR

 Minimum FEV₁ over 4-10 hrs post-saline challenge will be the minimum value of all the post-saline time points between 4 to 10 hours post-allergen challenge, inclusive of 4 hrs and 10 hrs time points i.e., minimum over 4 hrs, 4.5 hrs, 5 hrs, 5.5 hrs, 6 hrs, 6.5 hrs, 7 hrs, 7.5 hrs, 8 hrs, 8.5 hrs, 9 hrs, 9.5 hrs and 10 hrs. Note that the maximum FEV₁ value at each planned relative time point will be derived, where replicates are taken, for every subject and period, before the minimum values are calculated over the specified time period above. The minimum will be set to missing for the relevant challenge if either of the following occurs: 
 The subject did not receive the correct dose of study medication at any of the 8-weekly visits. A short-acting inhaled β-agonist is taken within 8 hours at any time prior to the challenge. If subject took rescue medication prior to the LAR period i.e. between 0 and 4 hours post-saline administration. The incorrect dose of allergen is administered for the respective BAC. Note that the dose of allergen used during the treatment period may be modified from the total dose received at screening for safety reasons at the discretion of the investigator. However, in this case, the modified dose used must be consistent for all follow up visits. In these cases only the baseline value will be set to missing (essentially removing the subject from any statistical modelling that has the baseline term as a covariate).
There may be other conditions that affect the LAR response. In such situations it may be necessary to set the respective response to missing. Such scenarios will be identified and documented before unblinding. Appropriate, sensitivity analyses may be conducted if other situations are noted following unblinding.
EAR
Weighted Mean EAR

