
 Weighted mean EAR will be calculated for FEV₁ using the linear trapezoidal rule as per LAR (see above) except using the appropriate EAR time points (i.e., 0 m, 5 m, 10 m, 15 m, 20 m, 30 m, 45 m, 1 hr, 1.5 hrs and 2 hrs). In the event that rescue medication is administered prior to the completion of the 2 hour FEV₁ assessment, the weighted mean will be calculated using only FEV₁ values up to the point of administration of rescue medication. This is considered the most appropriate derivation, given the natural self-limiting profile of the EAR.
Minimum EAR

 Minimum EAR will be calculated for FEV₁ as per LAR (see above) except using the appropriate EAR time points (see above) ie, 0-2 hrs post-saline challenge will be the minimum value of all the post-allergen challenge time points up to and including 2 hours post-allergen challenge i.e., minimum over 5 m, 10 m, 15 m, 20 m, 30 m, 45 m and 1 hr, 1.5 hrs and 2 hrs. Note, saline time point (i.e. 0 hr value) will not be included in this calculation.

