11.6.2.3 Handling of Missing Data for Statistical Analysis

The SAS PROC MCMC framework automatically assumes/implements a missing at random / multiple imputation approach if any of the supplied response variables are missing. This is deemed to be sufficient given the exploratory nature of the study. However, if a large proportion of data are missing then alternative approaches may be considered.

Several analyses are specified as being conditional on there being sufficient non-missing data to take place (e.g. Sputum and biomarkers with large proportions of LLQ values).

If model covariates are missing (e.g. Baseline) then the best approach will be selected on a case by case basis, but may involve omitting the record or imputing a response based on other data prior to fitting the observation model.

Given the exploratory nature of this study and the large number of endpoints it is not possible to pre-specify/cover all eventualities but any missing data approaches investigated would be documented in the CPSR and if deemed important included in the outputs as sensitivity analyses.

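### Minimum LAR has a set-to-missing rule for study medication that Weighted Mean LAR lacks; if *any* means one or more visits, the mITT run cannot test missed doses for Minimum LAR (minor)

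*SAP*

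**What the plan says.** SAP 11.5.4 gives a separate set-to-missing list for each primary endpoint.

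- **Minimum LAR.** Four triggers: a study-medication rule, "The subject did not receive the correct dose of study medication at any of the 8-weekly visits"; short-acting beta-agonist (SABA) use within 8 hours before the challenge; rescue between 0 and 4 hours; and an incorrect allergen dose.
- **Weighted Mean LAR.** The list opens "The weighted mean will be set to missing for the relevant challenge if any of the following occurs" and covers SABA within 8 hours, a changed allergen dose and rescue between 0 and 4 hours. Study medication is not mentioned.
- **Both.** A closing clause lets other conditions affecting the LAR lead to a missing value if documented before unblinding (for WM, before unblinding or database freeze).

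The primary analysis uses the PP population. Item 03 of SAP Appendix 1 is expected to exclude a subject on this ground: "Subject did not receive all 8 doses of planned medication (Placebo or GSK2245035". Exclusions are not automatic: "as described in the PDMP reviews and decisions will occur on a case by case basis". The mITT population is wider: "Comprise of all randomised subjects who receive at least one dose of study treatment and commence a BAC at follow-up".

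SAP 7.1.1 and 7.1.2 say the primary mITT run *may* be done. SAP 8.1.1 says the repeated-measures mITT run *will* be done when the populations differ. Appendix 13 already lists primary mITT outputs (Table 2.4, Figures 2.6 and 2.7, Listings 44 and 45) on that same condition.

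Protocol 6.11.1 asks subjects to withhold SABA for at least 6 hours before visits with lung function assessment or a challenge.

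**The concern.** Both primary endpoints come from the same FEV1 profile at the same challenge, so a dosing error is no more damaging to the minimum than to the weighted mean. A different rule needs a reason, and none is given.

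The bullet can also be read two ways, and a programmer must choose. If the choice is made after unblinding, it becomes data-dependent on a primary endpoint.

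What is at stake is the mITT run, the planned sensitivity analysis on the PP choice. If under-dosed subjects have no Minimum value, that endpoint will look stable to missed doses whatever those subjects' responses were, while WM can move. A reader could take the stability as evidence.

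**Working it through.** **1. The two readings of *any*.**

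| Reading | Who loses the Minimum value | Effect on mITT |
|---|---|---|
| None of the 8 visits correct | Almost nobody, since mITT requires at least one dose | Under-dosed subjects contribute to both endpoints |
| One or more visits not correct | Anyone with a missed or incorrect dose | Item 03 subjects contribute to WM but not to Minimum |

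**2. Why a blanked record adds nothing.** SAP 11.6.2.3 says PROC MCMC "automatically assumes/implements a missing at random / multiple imputation approach if any of the supplied response variables are missing". For model parameters θ, the posterior is proportional to prior(θ) × Π(observed) f(y|θ) × Π(missing) ∫f(y|θ)dy. Each integral equals 1, so the blanked records drop out. SAP 7.1.2 models each endpoint separately, so a subject's WM value cannot inform the missing Minimum.

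This was checked with a Gibbs sampler for model M3 (no centre term; the SAP's vague priors). The datasets had 20 PP subjects per arm plus missed-dose subjects assumed to have no drug effect. Each row is one illustrative dataset, not an average.

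| Missed-dose subjects added (active/placebo) | Median attenuation, PP | mITT, blanked | mITT, kept |
|---|---|---|---|
| 1/0 | -6.9% | -7.0% | -4.1% |
| 2/2 | 27.2% | 27.1% | 22.5% |
| 4/4 | 28.5% | 28.5% | 25.8% |
| 4/0 | 27.2% | 27.2% | 18.0% |

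PP and blanked mITT differ by at most 0.001 L in the treatment difference and 0.004 in the probability of any attenuation, which is simulation noise.

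**3. The plan's own figures.** Protocol 9.2.1 states a probability of success of about 78% (Minimum) and 81% (WM) with 20 completers per arm and a threshold of 0.7. Weighting Protocol Table 2 by degrees of freedom gives placebo means of -0.959 and -0.591 and variances of 0.188 and 0.130. The formula is Φ(attenuation × |mean| / √(2 × variance/20) − 0.524).

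- Minimum: 0.18 × 0.959 / 0.137 = 1.258, giving 76.8%.
- WM: 0.27 × 0.591 / 0.114 = 1.400, giving 81.0%.

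Both are close to the stated values.

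**4. Size if these subjects are kept.** Calibrating to the stated 78% and 81%:

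- Minimum: effect/SE = 0.772 + 0.524 = 1.297, so SE = 18/1.297 = 13.9 points.
- WM: effect/SE = 0.878 + 0.524 = 1.402, so SE = 27/1.402 = 19.3 points.

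The documents give no missed-dose rate. Assume k = 1, 2 or 3 of 20 active subjects are under-dosed and keep a share r of the effect, from 0 to 0.875 (7 of 8 doses, if benefit is proportional to doses). Expected attenuation = full attenuation × (1 − (k/20)(1 − r)).

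| k | Minimum (from 18%) | WM (from 27%) |
|---|---|---|
| 1 | 17.1 to 17.9% | 25.7 to 26.8% |
| 2 | 16.2 to 17.8% | 24.3 to 26.7% |
| 3 | 15.3 to 17.7% | 23.0 to 26.5% |

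The largest shifts (k = 3, r = 0) are 2.7/13.9 = 0.19 SE for Minimum and 4.05/19.3 = 0.21 SE for WM. For Minimum with k = 1, the posterior probability of any attenuation is 0.900 blanked and 0.891 to 0.901 kept. With k = 2 it is 0.897 blanked and 0.878 to 0.900 kept. All exceed 0.7.

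Single trials vary around these averages. In an ANCOVA simulation (8,000 runs; placebo mean -1.050, variance 0.218, baseline slope 0.5 assumed), restoring 1, 2 or 3 subjects moved the Minimum estimate with an SD of about 2.4, 3.5 or 4.4 points. Blanking suppresses that movement.

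**5. PP analysis.** If case-by-case review kept a missed-dose subject in PP, Minimum would lose one record that WM keeps. The SE rises by √((1/19 + 1/20)/(2/20)) = 1.013, and the probability of success goes from 78.0% to Φ(1.297/1.013 − 0.524) = 77.5%. Two such subjects in one arm give 77.0%.

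**6. SABA windows.** The protocol counts at least 6 hours back from the visit; the SAP counts 8 hours back from the challenge. The documents reviewed do not give the visit-to-challenge interval. If it is under 2 hours, SABA taken just outside 6 hours complies with the protocol yet falls inside the SAP's window, and both primary endpoints are then set to missing. The mismatch is 0 to 2 hours.

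**The case against.** The strongest case against is that little turns on this. The primary analysis is PP, and item 03 is expected to remove missed-dose subjects. All doses are given in clinic (Protocol 6.5) and confirmed by a second staff member (Protocol 6.6). SAP 7.1.1 calls the mITT run only a potential sensitivity analysis. The other-conditions clause could be used to align the endpoints. Under-dosed subjects' FEV1 profiles stay visible in the All Subjects displays (Figures 2.29 and 2.30, Listing 39). All of this stands, and it is why the point is minor. It does not remove the point: the clause is discretionary and does not name study medication, and a profile plot does not replace the model-based check.

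It is also fair that the bullet and item 03 do not match exactly. One concerns a correct dose, the other receipt of all eight. A subject given a wrong amount once meets the bullet but arguably not item 03, so the fix must cover that case.

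Four stronger readings are tempting, and the documents do not support them:

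- *The mITT run is worthless for Minimum LAR.* It still brings back subjects excluded from PP on other grounds.
- *Blanked records shift the percentage attenuation through baseline centring.* SAP 7.1.2 instructs: "do not use observations that will not contribute to the planned model when centering".
- *The early response is affected too.* Minimum EAR is calculated "as per LAR (see above) except using the appropriate EAR time points (see above) ie, 0-2 hrs post-saline challenge", but that this carries the blanking rule across is inference. EAR outputs are PP only, so the mITT argument has nothing to act on.
- *Large shifts such as 27.2% to 18.0% are likely.* That is one dataset with four active subjects and no retained effect, all assumed.

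**Conclusion.** The concern holds as a minor point. The two lists differ without a stated reason, and the bullet is ambiguous. On the one-or-more-visits reading, the mITT run adds essentially no information on missed doses for Minimum LAR. Because the bullet concerns dosing and not one particular challenge, the repeated-measures mITT run would lose the same information. On the none-of-the-visits reading there is almost no effect.

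A reader might infer that the primary result is biased or the trial's conclusion at risk. The documents do not support that: the PP result is largely unaffected, and no illustrated average shift exceeds 0.21 SE. The true size is unknown because no missed-dose rate is given. The figures rest on the assumed number of under-dosed subjects, their retained effect, and calibration to the stated 78% and 81%.

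The SABA mismatch is a separate inconsistency that can remove both primary endpoints for a subject who complied with the protocol.

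**What to change.** - Delete the study-medication bullet from the Minimum LAR derivation in SAP 11.5.4. State that Minimum and Weighted Mean use the same set-to-missing rules, and that missed or incorrect doses of study medication are handled only through PP membership.
- Reword item 03 of Appendix 1 to cover an incorrect dose as well as a missed one.
- If the difference is intended, give the reason and define *any*. Adding the bullet to WM would restore consistency, but on the one-or-more reading it would remove the missed-dose check for both endpoints.
- In SAP 7.1.1 and 7.1.2, change *may* to *will*, when PP and mITT differ, to match SAP 8.1.1 and the outputs already listed.
- Reconcile the SABA windows in Protocol 6.11.1 and SAP 11.5.4. This review does not say which applies.

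The cost of the first four is a few lines of SAP text and one programming rule, best settled before unblinding. The planned outputs do not change. PP membership changes only where the reworded item 03 catches an incorrect dose that the present wording does not. The mITT analysis of Minimum LAR will include outcomes from under-dosed subjects, as WM already does.

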11.5.5 Pharmacodynamic and Biomarker

Pharmacodynamic/Biomarker
TRL7 Induced Blood PD Biomarkers

 Fold changes should be computed relative to the Visit 1 pre-dose response (DV1 Pre-Dose), and if applicable, to the corresponding pre-dose value from that dosing visit (one value per subject per visit and time point combination). Fold changes should be computed using the imputed responses.
Sputum Differential Cell Counts

This section is based on understanding of the process and expected data items at time of RAP writing. Please consult with GSK Study Statistician at reporting time to confirm what manipulation steps are required, as process details may be changed in-stream as experience is gained (modifications wouldn't be captured via a formal RAP amendment but would be documented by the GSK study statistician via a note to file - if no changes are required then there will be no related note to file).
 
The following will be provided as source data from the eCRF. The vendor counting the slides would not have access to these values, hence why additional data manipulation is required by GSK Stats and Programming.
 
 'Total Cell Count (Total Non-Squamous Cells in sample)' [Equation 4 in the Sputum processing worksheet] 'Total Leukocytes Count (Total Non-Squamous Cells) per Gram of Selected Sputum Cells' [Equation 6 in the Sputum processing worksheet] '% Viable Leukocytes (% Viability of non-squamous cells)' [Equation 1 in the Sputum processing worksheet] 
Pertinent information to the planned data manipulations that the vendor counting the slides would return to GSK data management is:
 
 Was the slide rejected (Y/N) (and if Y the reasons for rejection) For each slide reader (up to three readers possible): Cell counts of the following types: eosinophils, neutrophils, macrophages, lymphocytes, BEC (bronchial epithelial cells) and squamous cells. These counts are from a representative set of cells counted on each slide (vendor expect to count a maximum of ~600 cells to get a minimum of ~400 non-squamous cells on each slide). The actual numbers of cells counted on the slide are also provided as "Total Cell Count" (sum of all cell types) and "Total non-squamous cell count" (sum of cell types; eosinophils, neutrophils, macrophages, lymphocytes and BEC). As a sanity check the supplied slide totals (per reader) should match those slide totals derived by hand using the individual cell type count results. 
Only two readers per slide are expected but the vendor may provide readings from a third reader if the results of the initial two readers are sufficiently different (according to the vendor's standard

Pharmacodynamic/Biomarker

operating procedure, currently > 10% for the major cell types eosinophils, macrophages and neutrophils). When >2 readers are supplied whichever pair of readers are closest to each other would be used in the subsequent derivations but data from all readers would be listed (and the reader pair indicated, e.g. R1R3 if Reader1 and Reader 3 used or R1R2 if Reader 1 and Reader 2 used).

The percentage of each leukocyte cell type observed on the slide will be derived for the i^{th} reader as follows (leukocyte cells are eosinophils, neutrophils, macrophages, lymphocytes and BEC)

$$\% \text{ Leukocyte Cell Type on Slide}_i = \frac{\text{Absolute Number of Leukocyte Cell Type}_i}{\text{Absolute Total Non - Squamous Cell Count}_i}$$

Prior to statistical analysis the results for each reader and slide would be “scaled up” to reflect the counts for the sample the slide was constructed with. This requires [Equation 6] information from the eCRF page.

The Absolute Leukocyte Cell Types Counts per gram of sputum for the i^{th} reader are derived as

Absolute Leukocyte Cell

$$\text{Type } \times 10^6 \text{ cells / g sputum}_i = \% \text{ Leukocyte Cell Type on Slide}_i * [\text{Equation 6}]$$

The geometric mean of the (two) readers would be derived and used in the statistical analyses that refer to the Absolute Cells/g sputum endpoint (separate variable for each cell type).

A new total non-squamous cell count variable will be created as the sum of the geometric mean's of the Leukocyte cell types. This total would be used to derive the percentage of each leukocyte cell type in the sample (ensures the percentages will sum to 100%) as “(Geo Mean Abs Leuk Cell Count / Total) * 100”.

These % endpoints would be used in statistical analyses (separate variable for each cell type)

The following scenarios may result in a sample being deemed as non evaluable (even if the vendor provided data back):

- Slide not read or rejected
- If the value entered in the eCRF for [Equation 1] $\leq 70\%$ (implying more than 30% of the non-squamous cells were not viable). Note: This threshold is study specific and may be altered upon review of the complete dataset in consultation with the GSK biology group
- $> 50\%$ squamous cells of the proportion counted
- < 200 total cells counted on the slide
- **Note:** When zero counts are observed for a cell type it complicates the derivation of the geometric means. A constant should be added onto all results in the dataset prior to deriving the reader geometric mean (separate value for the constant for each cell type). The constant should be set to half the smallest observed non-zero scaled up absolute count in the entire dataset for

Pharmacodynamic/Biomarker

that cell type, and if all values are zero in the dataset for the cell type then the variable would not be analysed but the means would be set to zero.

- The following is a worked example for two visits for the same subject.

Values entered on eCRF:

Visit	% Viable Leukocytes (% Viability of non-squamous cells) [Equation 1]	Total cell count (10^6 cells) (Total non-squamous cells in sample) [Equation 4]	Total Leukocytes count (Total non-squamous cell count) per gram of selected sputum (10^6 cells/g) [Equation 6]
1	85	1.062	7.080
2	74	1.11744	6.984

Values supplied by vendor

Visit	Reader	Eos	Neut	Mac	Lym	BEC	Squamous	Tot Non-Squ	Total cells
1	1	2	371	38	0	0	96	411	507
1	2	0	348	43	0	0	109	391	500
2	1	4	342	42	0	2	111	390	501
2	2	0	290	50	0	0	160	340	500

Derived % on slides

Visit	Reader	Eos	Neut	Mac	Lym	BEC			
1	1	0.49	90.27	9.25	0.00	0.00			
1	2	0.00	89.00	11.00	0.00	0.00			
2	1	1.03	87.69	10.77	0.00	0.51			
2	2	0.00	85.29	14.71	0.00	0.00			

Cell counts scaled up to sample and small constant added on to each to allow for zeros (e.g. Add to all scaled up BEC values the constant of $0.0178092 = 0.5 * 0.0051 * 6.984$)

Visit	Reader	Eos	Neut	Mac	Lym	BEC			
1	1	0.052038	6.391116	0.6549	0.00	0.018054			
1	2	0.017346	6.3012	0.7788	0.00	0.018054			
2	1	0.089281	6.12427	0.752177	0.00	0.053428			
2	2	0.017346	5.956654	1.027346	0.00	0.017809			

Pharmacodynamic/Biomarker

Geometric Means and Percentages used in statistical analyses (Lym has imputed Geo mean of zero)

Visit	Item	Eos	Neut	Mac	Lym	BEC		Tot Non-Squ	
1	Abs (10^6 cells/g sputum)	0.030044	6.345999	0.714168	0	0.017809		7.108265	
1	%	0.42	89.28	10.05	0	0.25			
2	Abs (10^6 cells/g sputum)	0.039353	6.03988	0.87906	0	0.030846		6.98914	
2	%	0.56	86.42	12.58	0	0.44			

[figure not shown]
WBC Differentials

- **Note:** When zero percentages are observed the corresponding cell count is also zero. Therefore if the count data require log transformations the constant to add on should be set at half the smallest observed non-zero count in the corresponding dataset

